6.1.2. Analysis Windows for Pulmonary Function Data Collected on Site

For pulmonary function tests conducted on site at study visits, the following analysis windows will be applied to include observations in deriving the analysis visits. When multiple eligible values are available in the same analysis window, the scheduled value, if available, will be used; and if the scheduled value is not available, then the value that is closest to the target date will be used.

Table 1: Analysis Windows for On-Site Pulmonary Function Test Parameters

[figure not shown]
Analysis Visit	Target Study Day	Analysis Window
Visit 4/Day 4	4	Day 1 post-dose to Day 7
Visit 5/Week 2	15	Day 8 to Day 21
Visit 6/Week 4	29	Day 22 to Day 42
Visit 7/Week 8	57	Day 43 to Day 70
Visit 8/Week 12	85	Day 71 to Day 99
Visit 9/Week 16	113	Day 99 to Day 126

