4.4. Study Days and Visits

For by-visit summaries, if there are multiple assessments at a postbaseline visit then the last non-missing assessment at that visit will be used for the summary (this includes scheduled and unscheduled assessments), except for triplicate ECG assessments (see Section 8.10 for further details).

Study visits are in Table 2 of the study protocol.

'Last Assessment' may be derived for analysis purpose and is defined as the last observed postbaseline data during the treatment period. For patients who withdraw from the study early, their data at the early withdrawal visit will be excluded from the by-visit summaries but will be included in the Last Assessment summaries.

Study days are numbered relative to the first day of the IMP administration. The start of treatment (day 1) is defined as the date on which a patient takes the first dose of the IMP, as

recorded on the case report form (CRF). Days will be numbered relative to treatment start (ie, ..., -2, -1, 1, 2, ...; with day 1 being the first day of the IMP administration and day -1 being the day before the first day of the IMP administration).

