6.2. Primary Efficacy Endpoint and Analysis

6.2.1. Definition

[figure not shown]
The primary endpoint is the change from baseline in clinic-based trough (pre-bronchodilator) morning FEV₁ at week 12.

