6.2.4.2. Supportive Analysis

The frequentist approach will be used for analyzing the primary efficacy endpoint as a supportive analysis. The primary estimand with respect to treatment condition, study population, efficacy endpoint and ICEs along with the ICE handling strategies will be applied. Both the multiple imputation method and the reference-based multiple imputations method will be used to handle

the missing data. The population-level summary statistics will be the combined least squares means in the treatment groups and the combined least squares mean treatment differences derived from analyses of the multiply imputed datasets using the mixed-effects model for repeated measures (MMRM).

The MMRM model will include baseline morning trough FEV₁, the randomization stratification factors (prior therapy use and absolute eosinophil count at screening), visit (weeks 2, 4, 8, 12, and 16), treatment group, and visit-by-treatment group interactions. Contrasts for pairwise treatment comparisons of interest will be constructed. The unstructured (UN) covariance structure will first be used; however, in the case UN covariance structure does not converge, the compound symmetry (CS) covariance structure will be used.

The Rubin's method will be used to combine estimates from multiply-imputed datasets. The final estimated treatment differences will be presented together with the 2-sided 90% CI and p-values.

[figure not shown]
MI steps and SAS example codes are as follows:

Step 1: Following observations will be considered as “analysis dropouts” and be excluded from the analysis (set to missing)

- observations after the use of asthma maintenance medications (regardless of availability of data obtained afterwards);
- observations that occurred after the diagnosis of COVID-19 infections.

[figure not shown]
For all early dropouts and “analysis dropouts”, regardless of assigned treatment arm, missing imputation will be based on data from the placebo-treated patients (eg, reference-based imputation).

Step 2: Missing data will be imputed with 100 imputations using multiple imputation and reference-based multiple imputations. The same sample codes for imputations for the Bayesian analysis will be used (see Section 6.2.2 and Section 6.2.4.1, respectively).

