6.3.4. Changes From Baseline in Percentage of Asthma Control Days (No Symptoms and No Rescue Medication Use) Over 12 Weeks From Week 1 Through 12 and Over 16 Weeks From Week 1 Through 16

An asthma control day is defined as a day on which the patient uses zero puffs of inhaled SABA, has no night-time awakenings, and experiences no asthma exacerbations.

The post-baseline analysis window for over 12 weeks will be from the first day of IMP up to the day 84. The post-baseline analysis window for over 16 weeks will be from the first day of IMP up to the day 112. Baseline window will include days up to the first dose of IMP.

Percentage of asthma control days in each analysis window will be calculated as

$$(\sum \text{asthma control days in an analysis window} / \text{number of non-missing e-diary days during the analysis window}) * 100$$

The changes from baseline in percentage of asthma control days over 12 weeks (up to day 84) and over 16 weeks (up to day 112) will be analyzed, respectively, using analysis of covariance (ANCOVA) including baseline percentage of asthma control days, randomization stratification factors, and treatment group in the model.

6.3.5. Change From Baseline in Clinic-Based Standardized Baseline-Adjusted Morning Trough FEV₁ at Week 16

The analysis will be based on data collected at site visits. FEV₁ measures at visit 1/screening, visit 3/DoR, visit 4/week 1, visit 5/week 2, visit 6/week 4, visit 7/week 8, visit 8/week12, and visit 9/week 16 or the early withdrawal visit. The analysis will include post-baseline data up to the visit 6/week 16. Baseline will be the last measure before the first dose of IMP.

The change from baseline in clinic-based morning trough FEV₁ at week 16 will be analyzed using MMRM method in a manner analogous to the analysis as described in Section 6.3.2. Baseline clinic-based morning trough FEV₁ will be used in model. WEEK will denote to the visit.

For model-based results, only week 16 results will be displayed. Summary statistics will be provided by visit/week.

6.3.6. Proportions of Patients Who Achieve Clinic-Based FEV₁ \geq 80% Predicted at Weeks 12, 16, and at Endpoint

The percent of predicted FEV₁ will be measured by handheld device. The analysis will be based on data collected at site visits and will be applied in patients with baseline FEV₁ $<$ 80% Predicted.

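### SAP Table 1 places Day 99 in both the week 12 and the week 16 spirometry windows, and no rule says which visit takes a value from that day

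*SAP*

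**What the plan says.** Table 1 in SAP section 6.1.2 maps clinic spirometry to analysis visits by study day. The windows that matter here are:

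- week 8, target Day 57: "Day 43 to Day 70"
- week 12, target Day 85: "Day 71 to Day 99"
- week 16, target Day 113: "Day 99 to Day 126"

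The section gives one selection rule: "When multiple eligible values are available in the same analysis window, the scheduled value, if available, will be used". Failing a scheduled value, the value nearest the target day is taken. The section does not say what happens to a value that lies in two windows.

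Both visits feed named analyses. Section 6.2.1 defines the primary endpoint at week 12: "The primary endpoint is the change from baseline in clinic-based trough (pre-bronchodilator) morning" FEV₁. Section 6.3.5 analyses the same measure at week 16 as a secondary endpoint. The supportive model in section 6.2.4.2 treats the two as separate repeated measures, with terms for "visit (weeks 2, 4, 8, 12, and 16), treatment group, and visit-by-treatment group interactions". The SAP introduction says that the SAP takes precedence over the protocol, so Table 1 governs.

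**The concern.** An analysis window should send each measurement to one visit. Here a single Day 99 measurement qualifies for two, and the written rule cannot separate them. Two things follow.

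First, one reading could enter the repeated-measures model as if it were two, and could supply the week 16 secondary endpoint with a value already used at week 12.

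Second, take a patient with no other week 12 value. Whether Day 99 belongs to week 12 decides whether the primary endpoint is observed or is filled by the multiple imputation of section 6.2.2. That should be settled in the SAP before unblinding and not left to whoever programs the windows.

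**Working it through.** The plan states no figure on this point that could be reproduced. The check is a count of days against windows.

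**Inputs.** Windows and targets come from SAP Table 1. Visit timing comes from protocol Table 2: Visit 8 on Day 84±2 and Visit 9 on Day 112±2, counted from Day 0. SAP section 4.4 numbers days "with day 1 being the first day of the IMP administration", so one day is added to convert.

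**Step 1: bounds and lengths** (length = end − start + 1).

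| Visit | Target | Window | Length | Offsets from target |
|---|---|---|---|---|
| Visit 4 | 4 | 1–7 | 7 | −3/+3 |
| Week 2 | 15 | 8–21 | 14 | −7/+6 |
| Week 4 | 29 | 22–42 | 21 | −7/+13 |
| Week 8 | 57 | 43–70 | 28 | −14/+13 |
| Week 12 | 85 | 71–99 | 29 | −14/+14 |
| Week 16 | 113 | 99–126 | 28 | −14/+13 |

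The lengths sum to 7 + 14 + 21 + 28 + 29 + 28 = 127, but Days 1 to 126 are only 126 days, so one day is counted twice. The boundaries 7/8, 21/22, 42/43 and 70/71 are disjoint. The last is 99/99, so the repeated day is Day 99.

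**Step 2: could nearness to target settle it?** 99 − 85 = 14 and 113 − 99 = 14. Day 99 is equally far from both targets, so extending the nearest-to-target rule across windows would not break the tie.

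**Step 3: what the table does elsewhere.** Midpoints between adjacent targets are (15 + 29)/2 = 22, (29 + 57)/2 = 43 and (57 + 85)/2 = 71. Each of these days is the first day of the later window. The next midpoint is (85 + 113)/2 = 99, so the same pattern puts Day 99 in week 16 only. (The first boundary, between Visit 4 and week 2, does not follow the midpoint: it lies at 7/8 and the midpoint is 9.5.)

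**Step 4: when the overlap matters.** Visits held on time fall on study Days 84 + 1 ± 2 = 83–87 and 112 + 1 ± 2 = 111–115. A Day 99 test is therefore early, late or unscheduled. With Table 1 as written:

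| Other clinic values | Use of the Day 99 value |
|---|---|
| On-time Visit 8 and on-time Visit 9 | neither visit |
| On-time Visit 8, no Visit 9 | week 16 only |
| No Visit 8, on-time Visit 9 | week 12 only |
| No other value in either window | both visits |

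Only the last row gives double use.

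**Step 5: after the correction.** With week 12 at Days 71–98, its length is 28 and its offsets are −14/+13, matching weeks 8 and 16. The lengths sum to 126, and every day from 1 to 126 lies in exactly one window.

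**The case against.** The strongest reply is that this is a one-digit slip with almost no practical reach. Most of that stands.

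- A reader might infer that any Day 99 value fills both visits. The documents do not support this, because a scheduled or closer value displaces it in either window.
- The obvious routes to a Day 99 test do not by themselves give double use. Under protocol section 3.1, Visit 9 procedures are brought forward when maintenance treatment changes after Visit 8. If a Visit 8 value was obtained, it already holds week 12. If an outbreak delays Visit 8 to Day 99 (protocol Appendix N), a later Visit 9 value holds week 16. If the delay was the patient's own moderate or severe COVID-19, SAP section 1.3.1 drops values after diagnosis from the primary analysis.
- Early withdrawal on Day 99 with Visit 8 missed is the more plausible route. SAP section 4.4 keeps early-withdrawal data out of by-visit summaries, yet section 6.3.5 lists that visit among the FEV₁ measures, so the route is not clearly closed.
- Spirometry is not among the listed procedures for unscheduled visits in protocol Appendix B. It is possible only at the investigator's discretion.
- A reader might also infer that double use distorts the primary result. Copying a Day 99 value into week 16 leaves the observed week 12 value as it was. Whether week 16 data inform the week 12 imputation cannot be judged, because the detail of that model in section 6.2.2 is redacted.

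What the reply does not remove is the overlap itself, or the lack of any sentence that assigns a Day 99 value to one visit.

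**Conclusion.** The point holds as a minor error in an operative rule. Table 1 puts Day 99 in two windows, one of which defines the primary endpoint, and neither the selection rule nor distance from target resolves it. One value could serve both visits, but only for a patient tested in clinic on exactly Day 99 with no scheduled or closer value in either window. Separately, the status of such a value at week 12, observed or left to imputation, is not settled.

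The expected effect is negligible. The documents give no basis for a patient count, so none is offered. Double use would fall mainly on the week 16 secondary endpoint and the supportive model. It is not a material threat to the primary result.

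The conclusion assumes that the signed SAP prints 99 as the end of the week 12 window. If it prints 98, the point falls away.

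**What to change.** In SAP Table 1, change the week 12 window to Day 71 to Day 98 and leave week 16 at Day 99 to Day 126. A sentence stating that each value is assigned to one analysis visit only would be a useful addition.

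Starting week 16 at Day 100 would also remove the overlap, but it is not an equivalent change. It would keep a Day 99 value eligible for the primary endpoint, whereas ending week 12 at Day 98 makes it a week 16 value. The first option is preferable because it follows the table's own pattern. Its consequence should be accepted knowingly: a patient whose only candidate week 12 value is from Day 99 would have week 12 imputed.

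The cost is one number in the SAP and the matching line in the window derivation, made before unblinding. No data collection, sample size or power figure is affected.

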6.2. Primary Efficacy Endpoint and Analysis

6.2.1. Definition

[figure not shown]
The primary endpoint is the change from baseline in clinic-based trough (pre-bronchodilator) morning FEV₁ at week 12.

6.2.3. Subgroup Analysis

Sub-group analyses will be performed on the primary endpoint and selected secondary endpoints for

- gender (male vs female)
 - race (white vs other races)
 - age group (<65 years vs \geq 65 years)
 - Randomization factor per IRT: eosinophil count (<400 cells/uL vs. \geq 400 cells/uL)Randomization factor per IRT: prior asthma maintenance therapy (ICS alone or low dose ICS/LABA vs. medium and high dose ICS/LABA)

The selected secondary endpoints are

- overall weekly well-controlled asthma status defined by the asthma control composite score and weekly asthma control status (Yes versus No) over 12 weeks from week 1 through 12 and over 16 weeks from week 1 through 16
 - overall changes from baseline in the weekly average of daily morning trough (pre-rescue bronchodilator) FEV₁ as measured by a handheld device over 12 weeks from week 1 through 12 and over 16 weeks from week 1 through 16
 - overall changes from baseline in weekly average of rescue medication use over 12 weeks from week 1 through 12 and over 16 weeks from week 1 through 16
 - changes from baseline in percentage of asthma control days (no symptoms and no rescue medication use) over 12 weeks from week 1 through 12 and over 16 weeks from week 1 through 16

- change from baseline in clinic-based standardized baseline-adjusted morning trough FEV₁ at week 16

For continuous endpoints, the same MMRM analysis as described in Section 6.3.2 will be applied, by each subgroup variable. For the binary endpoint of weekly asthma control status, the analysis described in Section 6.3.1 will be applied, by each subgroup variable. The final estimated treatment differences will be presented together with the 2-sided 95% CI and p-values by the subgroup variables using the Forest Plot.

6.2.4. Sensitivity/Supportive Analysis for the Primary Efficacy Endpoint

6.2.4.1. Sensitivity Analyses

As sensitivity analyses, the primary efficacy analysis and supportive analysis will be repeated using the PP population and ITT population if the difference between mITT and ITT is more than 5%.

In order to assess the robustness of the results under a missing not at random (MNAR) mechanism, another sensitivity analysis using the reference-based multiple imputation method as the missing data handling method will be conducted. The reference-based multiple imputations method ([Mallinckrodt et al 2017](#)) imputes missing data based on regression models from the placebo-treated patient data, representing a missing not at random (MNAR) mechanism. A sample SAS code for the reference-based multiple imoutations is given below:

6.2.4.2. Supportive Analysis

The frequentist approach will be used for analyzing the primary efficacy endpoint as a supportive analysis. The primary estimand with respect to treatment condition, study population, efficacy endpoint and ICEs along with the ICE handling strategies will be applied. Both the multiple imputation method and the reference-based multiple imputations method will be used to handle

the missing data. The population-level summary statistics will be the combined least squares means in the treatment groups and the combined least squares mean treatment differences derived from analyses of the multiply imputed datasets using the mixed-effects model for repeated measures (MMRM).

The MMRM model will include baseline morning trough FEV₁, the randomization stratification factors (prior therapy use and absolute eosinophil count at screening), visit (weeks 2, 4, 8, 12, and 16), treatment group, and visit-by-treatment group interactions. Contrasts for pairwise treatment comparisons of interest will be constructed. The unstructured (UN) covariance structure will first be used; however, in the case UN covariance structure does not converge, the compound symmetry (CS) covariance structure will be used.

The Rubin's method will be used to combine estimates from multiply-imputed datasets. The final estimated treatment differences will be presented together with the 2-sided 90% CI and p-values.

[figure not shown]
MI steps and SAS example codes are as follows:

Step 1: Following observations will be considered as “analysis dropouts” and be excluded from the analysis (set to missing)

- observations after the use of asthma maintenance medications (regardless of availability of data obtained afterwards);
- observations that occurred after the diagnosis of COVID-19 infections.

[figure not shown]
For all early dropouts and “analysis dropouts”, regardless of assigned treatment arm, missing imputation will be based on data from the placebo-treated patients (eg, reference-based imputation).

Step 2: Missing data will be imputed with 100 imputations using multiple imputation and reference-based multiple imputations. The same sample codes for imputations for the Bayesian analysis will be used (see Section 6.2.2 and Section 6.2.4.1, respectively).

Where TRTP denotes the planned treatment group; AVISIT denotes visit/week; RSTRATA the randomization stratification; BASE denotes the baseline FEV₁; CHG_i denotes the change from baseline at each visit based on imputed data.

Step 4: The results from the 100 analyses from Step 3 will be combined using Rubin's formulae. The least square (LS) mean estimates for the mean change from baseline to each time point, as well as the difference of the estimates between the active and placebo group, with the corresponding SE, p-value and associated 95% CI will be provided.

6.2.4.3. Supplementary Analysis

A supplementary analysis using all data, including retrieved observations following alternative asthma medication use will be run to assess the robustness of study results to the secondary estimand, defined in Section 1.3. The primary Bayesian analysis and the frequentist supportive analysis will be used.

6.3. Secondary Efficacy Endpoints and Analyses

The key secondary efficacy endpoints are listed in Section 1.1. Analyses will be based on the mITT analysis set.

6.3.1. Overall Weekly Well-Controlled Asthma Status Defined by the Asthma Control Composite Score and Weekly Asthma Control Status (Yes Versus No) From Week 1 Through 12 and Overall Weekly Well-Controlled Asthma Status From Week 1 Through 16

The weekly asthma control status (Yes or No) is the derived asthma control composite score based on the following criteria (also see Section 6.1.7 of the study protocol):

1. Two or more of the following criteria are fulfilled
 - ≤ 2 days with a daily asthma symptom score >1
 - ≤ 2 days of albuterol/salbutamol used as rescue medication up to a maximum of 4 occasions per week (multiple occasions per day are counted as separate occasions)
 - morning FEV₁ $\geq 80\%$ predicted for each day (by handheld device)

and

[figure not shown]
2. Both of the following criteria are fulfilled:
 - no night-time awakenings due to asthma
 - no use of asthma maintenance medications

For the analysis purpose, weekly analysis windows (weeks 1 to 16) will be derived as described in Section 6.1.1. The asthma control status in each weekly analysis window will be Yes if the conditions 1 and 2 above met, No otherwise.

The overall weekly asthma control status from week 1 through 12 or week 1 through 16 will be analyzed using the repeated measures logistic regression with treatment group, baseline status, and the randomization stratification factor, week, and week-by-treatment group interactions in the model and with the unstructured (UN) covariance structure. In the case UN covariance structure does not converge, the compound symmetry covariance structure (CS) will be used. All weekly asthma control statuses from weeks 1 to 16 will be included in the repeated measures model.

To estimate the probability of overall asthma control over 12 weeks in each treatment group, or to conduct a comparison between the treatment groups, appropriate contrast statements need to be used.

6.3.2. Overall Changes From Baseline in the Weekly Average of Daily Morning Trough (Pre-Rescue Bronchodilator) FEV₁ as Measured by a Handheld Device Over 12 Weeks From Week 1 Through 12 and Over 16 Weeks From Week 1 Through 16

[figure not shown]
The FEV₁ is measured by a handheld device daily. The weekly analysis window will be derived as described in Section 6.1.1. The daily average within each weekly analysis window will be

derived using formula [1] in Section 6.1.1. Measurement values taken within 4 hours of a rescue bronchodilator use will be set to missing.

The endpoints will be analyzed using a MMRM including baseline FEV₁, randomization stratification factors, week, treatment group, and week-by-treatment group interactions in the model with UN covariance structure. In the case UN covariance structure does not converge, the compound symmetry (CS) covariance structure will be used.

One MMRM model will be run including all 16-week data. The overall and by-week results will be derived using appropriate contrast statements and presented. The endpoint will be measured by the overall results. LS mean and SE for each treatment group, LS means and corresponding 95% confidence intervals for the treatment differences (active - placebo), and the associated p-values from the overall results for treatment comparisons.

Descriptive statistics from each week will be provided.

[REDACTED]

6.3.3. Overall Changes from Baseline in Weekly Average of Rescue Medication Use Over 12 Weeks From Week 1 Through 12 and Over 16 Weeks From Week 1 Through 16

The number of times asthma rescue medication (number of inhalations/puffs) used will be recorded on e-diary.

The post-baseline analysis window for over 12 weeks will be from the first day of IMP up to the day 84. The post-baseline analysis window for over 16 weeks will be from the first day of IMP up to the day 112. Baseline window will include days up to the first dose of IMP. Data in each analysis window will be normalized to 7 days as

$$(\sum \text{rescue medication uses during an analysis window} / \text{number of non-missing e-diary days during the analysis window}) * 7$$

The changes from baseline in weekly average of rescue medication over week 12 and over week 16 will be calculated and analyzed using Wilcoxon rank-sum test stratified on randomization stratification factors, respectively. The Hodges-Lehmann estimator of the treatment differences (TEV43275 treatment groups vs placebo) will be presented.

[REDACTED]

[REDACTED]

[REDACTED]

[REDACTED]

[REDACTED]

[REDACTED]

[REDACTED]

6.3.4. Changes From Baseline in Percentage of Asthma Control Days (No Symptoms and No Rescue Medication Use) Over 12 Weeks From Week 1 Through 12 and Over 16 Weeks From Week 1 Through 16

An asthma control day is defined as a day on which the patient uses zero puffs of inhaled SABA, has no night-time awakenings, and experiences no asthma exacerbations.

The post-baseline analysis window for over 12 weeks will be from the first day of IMP up to the day 84. The post-baseline analysis window for over 16 weeks will be from the first day of IMP up to the day 112. Baseline window will include days up to the first dose of IMP.

Percentage of asthma control days in each analysis window will be calculated as

$$(\sum \text{asthma control days in an analysis window} / \text{number of non-missing e-diary days during the analysis window}) * 100$$

The changes from baseline in percentage of asthma control days over 12 weeks (up to day 84) and over 16 weeks (up to day 112) will be analyzed, respectively, using analysis of covariance (ANCOVA) including baseline percentage of asthma control days, randomization stratification factors, and treatment group in the model.

6.3.5. Change From Baseline in Clinic-Based Standardized Baseline-Adjusted Morning Trough FEV₁ at Week 16

The analysis will be based on data collected at site visits. FEV₁ measures at visit 1/screening, visit 3/DoR, visit 4/week 1, visit 5/week 2, visit 6/week 4, visit 7/week 8, visit 8/week12, and visit 9/week 16 or the early withdrawal visit. The analysis will include post-baseline data up to the visit 6/week 16. Baseline will be the last measure before the first dose of IMP.

The change from baseline in clinic-based morning trough FEV₁ at week 16 will be analyzed using MMRM method in a manner analogous to the analysis as described in Section 6.3.2. Baseline clinic-based morning trough FEV₁ will be used in model. WEEK will denote to the visit.

For model-based results, only week 16 results will be displayed. Summary statistics will be provided by visit/week.

6.3.6. Proportions of Patients Who Achieve Clinic-Based FEV₁ \geq 80% Predicted at Weeks 12, 16, and at Endpoint

The percent of predicted FEV₁ will be measured by handheld device. The analysis will be based on data collected at site visits and will be applied in patients with baseline FEV₁ $<$ 80% Predicted.

For analysis purposes, a dichotomous scale of 'Yes' (FEV₁ \geq 80% Predicted) or 'No' (FEV₁ $<$ 80% Predicted) will be derived and analyzed using the repeated measures logistic regression model. Baseline percent of predicted FEV₁ will be used in the model. Weeks/visits include site visits visit 8/week 12 , visit 9/week 16 , and "endpoint". Summary statistics will be provided.

[REDACTED]

[REDACTED]

[REDACTED]

[REDACTED]

[REDACTED]

6.3.7. Proportions of Patients Who Achieve Forced Expiratory Flow at 25% to 75% of FVC (FEF_{25-75}) $\geq 70\%$ Predicted at Weeks 12, 16, and at Endpoint

The forced vital capacity (FVC) is the volume of air that can be forcibly blown out after full inspiration, measured in liters. The FEF_{25-75} is the forced expiratory flow at 25% to 75% of FVC and will be measured by handheld device.

For analysis purpose, a dichotomous score of 'Yes' ($FEF_{25-75} \geq 70\%$) or 'No' ($FEF_{25-75} < 70\%$) will be derived and analyzed using the repeated measures logistic regression model in a manner analogous to the analysis as described Section 6.3.1. Baseline FEF_{25-75} will be used in the model. Weeks/visits include all post-baseline site visits up to visit 8/week 12 (for Week 12 analysis) or up to visit 9/week 16 (for Week 16 analysis). Summary statistics will be provided by visit/week.

